7.2.2 Secondary Endpoints

- Determination of ORR, DOR, OS, and PFS (Section 7.6.2).
- Determination of PK parameters (Section 7.6.3) for ADCT-402 (total antibody; DAR \geq 0), PBD-conjugated antibody (DAR \geq 1), and free warhead SG3199.
- Measurement of ADAs to ADCT-402 before, during, and after treatment with ADCT-402 (Section 7.6.3).

7.3 Sample Size Calculations

This is a Phase I study with a maximum total sample size of 70 patients. It is expected that Part 1 will enroll up to 40 patients and Part 2 will enroll up to 30 patients. Patients will be enrolled in Part 2 of the study in cohorts of approximately 10. Based on a true AE rate of 15%, there is 80% confidence that one AE will be observed for the 10 patients enrolled. The DESC will make

ADCT-402-102 Protocol Amendment 3

recommendations with regard to the intended differences between these cohorts, e.g. tumor subtypes, dosing regimen or dose levels, as well as the number of these cohorts, taking into account the limit on the overall number of patients as specified above and safety/efficacy data observed up to that decision point.

7.4 Analysis Sets

Six analysis sets will be used in this study:

- The Safety analysis set will consist of all patients who receive study drug.
- The DLT-evaluable analysis set will consist of all patients in Part 1 who receive study drug and excludes patients who discontinue from the study drug during Cycle 1 without experiencing a DLT.
- The Efficacy analysis set will consist of all patients with valid baseline data who receive at least 2 doses of study drug or who have documented progression of disease at any time after the first dose of study drug.
- The PK analysis set will consist of all patients who receive study drug and have sufficient concentration data for PK analysis.
- The PD analysis set will consist of all patients who receive study drug and have sufficient data available for analysis.

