3.2 Dose-Escalation

In Part 1, dose-escalation will be conducted according to a 3+3 design (Figure 2). The initial dose of ADCT-402 will be 15 μ g/kg (Dose Level 1), and the highest allowed dose will be 600 μ g/kg. The potential dose levels are described in Table 1 and Table 2.

ADCT-402-102 Protocol Amendment 3

Table 1. Planned Dose Levels for ADCT-402 (Q3W Administration)

Dose Level	Dose of ADCT-402	Dose Level	Dose of ADCT-402
1	15 μg/kg	9	300 μg/kg
2	30 μg/kg	10	350 μg/kg
3	60 μg/kg	11	$400~\mu g/kg$
4	90 μg/kg	12	$450~\mu g/kg$
5	120 μg/kg	13	500 μg/kg
6	150 μg/kg	14	550 μg/kg
7	200 μg/kg	15	$600~\mu g/kg$
8	250 μg/kg		

Table 2. Planned Dose Levels for ADCT-402 (QW Administration)

Dose of ADCT-402	Dose Level	Dose of ADCT-402
5 μg/kg	7	75 μg/kg
10 μg/kg	8	100 μg/kg
20 μg/kg	9	125 μg/kg
30 μg/kg	10	150 μg/kg
40 μg/kg	11	175 μg/kg
50 μg/kg	12	200 μg/kg
	5 μg/kg 10 μg/kg 20 μg/kg 30 μg/kg 40 μg/kg	5 μg/kg 7 10 μg/kg 8 20 μg/kg 9 30 μg/kg 10 40 μg/kg 11

The dose-limiting toxicity (DLT, Section 6.3.1) observation period for dose-escalation is 1 cycle. The first patient enrolled into the study at 15 μ g/kg (Dose Level 1) must be observed for 7 days for occurrence of adverse events (AEs) prior to treating the second patient in the study. Patients will be entered sequentially to each dose level.

For each dose level, if none of the first 3 patients at that level experiences a DLT, new patients may be entered at the next higher dose level. If 1 of 3 patients experiences a DLT, up to 3 more patients are to be treated at that same dose level. If none of the additional 3 patients at that dose level experiences a DLT, new patients may then be entered at the next higher dose level. However, if 1 or more of the additional 3 patients experiences a DLT, then no further patients are to be started at that dose level and the preceding dose is identified as the MTD. The MTD;

ADCT-402-102 Protocol Amendment 3

therefore, is defined as the highest dose level at which none of the first 3 treated patients, or no more than 1 of the first 6 treated patients, experiences a DLT.

No intra-patient dose-escalation is allowed.

[figure not shown]

Figure 2. Schematic Representation for Dose-Escalation (3+3) Design

Abbreviations: DLT, dose-limiting toxicity; MTD, maximum tolerated dose; \leq , less than; \geq greater than or equal to.

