The number of dose levels will depend on the emergent toxicity profile of ADCT-402 and will be decided by the DESC (Section 6.3.2); PK, and PD evaluations may also inform decision making.

Every 3 Week (Q3W) Administration

Patients will be given ADCT-402 on Day 1 of each 3-week treatment cycle.

Weekly (QW) Administration

Patients will be given ADCT-402 QW on Days 1, 8 and 15 of each 3-week (21-day) treatment cycle.

The first dose level for the QW dosing will be based on the safety and tolerability of patients who have been treated on the every 3-week (Q3W) schedule. The first 3 patients will be given a cumulative dose each cycle that is comparable to (but not higher than) the highest dose tested at the Q3W dose schedule at which 3 patients completed the DLT observation period without a DLT. For example, if the highest Q3W dose tested at which 3 patients did not experience a DLT was cohort 150 μ g/kg, the first cohort to receive QW dosing will receive 50 μ g/kg each week for 3 weeks.

A patient will maintain the same treatment schedule throughout the duration of the trial.

ADCT-402-102 Protocol Amendment 3

Weekly dosing will be implemented at the discretion of the DESC (and in accordance with local ethics committee approvals). Once a patient achieves CR/CRi, frequency or dose may be adjusted by the DESC based on emerging safety, efficacy and PK profile.

The trial will be continuously monitored for emerging safety, efficacy and/or PK profile and the DESC will determine if it is appropriate to maintain a QW schedule, revert to a Q3W schedule, or test other dosing regimens.

During Part 1, the DESC may expand enrollment at doses below the current dose level as part of the dose-escalation process. Additional patients may only be added at a lower dose level provided there is at least 1 patient who has achieved a PR (Section 6.1) or better. No more than 10 patients in total can be treated at any dose level unless \geq 3 of the 10 patients have achieved a PR or better

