4.2.3 Patient Replacements

Any patient in Part 1 who discontinues before completion of the first treatment cycle, for any reason other than a DLT, is to be replaced.

ADC Therapeutics ADCT-402
ADCT-402-102 Protocol Amendment 3

5 Study Treatments

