5.4 Dose Delays and Modifications

Patients will receive the first 2 cycles of ADCT-402, irrespective of blood count recovery. For patients achieving a CR/CRi, the subsequent cycle would be delayed until peripheral blood count recovery (absolute neutrophil count [ANC] $>500 \times 10^9$ /L and/or platelets $>50 \times 10^9$ /L).

The Investigator may suspend ADCT-402 dosing for up to 21 days for any patient who experiences a protocol-defined DLT after Cycle 1 (the defined DLT observation period). At the discretion of the Investigator, the dose may also be delayed for up to 21 days for any toxicity that does not meet DLT criteria. Resumption of dosing with ADCT-402 after suspension is at the discretion of the Investigator, based on assessment of the patient's clinical condition and whether or not the patient is deriving potential clinical benefit from treatment with ADCT-402. Following recovery to Grade 1 or to baseline Grade, treatment with ADCT-402 may resume at the Investigator's discretion.

Patients who resume treatment following a dose delay may, at the discretion of the Investigator, have their dose reduced by 1 dose level. If toxicity recurs at a severity that would mandate a dose delay, then the dose may be further reduced 1 dose level. If toxicity recurs at such level, then the patient is to be discontinued from treatment. Dose re-escalation is allowed at the Investigator's discretion, at maximum to the dose level the patient was initially assigned to.

Dose frequency may be adjusted according to individual patient response as described in Section 3.2.

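### Under weekly dosing no rule requires a minimum Cycle 1 exposure, so if delayed infusions are skipped, a patient given one of three can count as DLT-free and help clear a dose level

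*Protocol*

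**What the plan says.** **Schedule and DLT window.** Protocol 3.2 sets the weekly regimen: "Patients will be given ADCT-402 QW on Days 1, 8 and 15 of each 3-week (21-day) treatment cycle". The DLT window is defined by time only: the "observation period for dose-escalation is 1 cycle".

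**Escalation and MTD.** Protocol 3.2 says that "if none of the first 3 patients at that level experiences a DLT, new patients may be entered at the next higher dose level". After one DLT in three, up to three more patients are treated, and the rule then reads: "If none of the additional 3 patients at that dose level experiences a DLT, new patients may then be entered at the next higher dose". The MTD is the highest level with no DLT in the first three treated patients, or at which "no more than 1 of the first 6 treated patients, experiences a DLT".

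**Replacement and evaluability.** Under Protocol 4.2.3 a Part 1 patient "who discontinues before completion of the first treatment cycle, for any reason other than a DLT, is to be replaced". Under Protocol 7.4 the DLT-evaluable set takes Part 1 patients who receive study drug and "excludes patients who discontinue from the study drug during Cycle 1 without experiencing a DLT". Both rules act on discontinuation alone.

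**Delays.** Protocol 5.4 says that, at the Investigator's discretion, "the dose may also be delayed for up to 21 days for any toxicity that does not meet DLT criteria". It makes no exception for Cycle 1. Protocol 4.2.1 requires withdrawal only when a delay passes 21 consecutive days counted from the planned Day 1 dose, and allows a Sponsor-approved exception.

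**SAP.** The trial stopped before dose escalation was complete (SAP 3.3). The only analysis set defined is the Safety set (4.1), and DLTs are listed, not tabulated (4.8.1). Number of infusions, cumulative dose and relative dose intensity are summarized, and infusion details are listed (4.7.1).

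**The concern.** With dosing every three weeks, the only Cycle 1 dose falls on Day 1. A patient still on drug at the end of the cycle has had the planned dose, partial infusions aside. Weekly dosing breaks that link, because a patient can remain on study and complete 21 days having received one infusion, or two. None of the rules separates that patient from one who tolerated all three.

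At stake is what zero DLTs in three patients means. A patient who carried less drug than the level specifies had less chance of a DLT but is counted as a full observation, so the error favours clearing the level. Toxicity is one of the permitted reasons for delay, so it is plausible that this happens more often at less tolerable levels. The documents give no figures on that.

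The same section does set an exposure floor elsewhere: the Efficacy set requires at least two doses or documented progression. The DLT-evaluable set has no counterpart.

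**Working it through.** **The plan's own figure.** The documents give no operating characteristics for the 3+3 design. The only probability in Protocol 7.3 concerns Part 2: an AE with a true rate of 15% should be seen among 10 patients with 80% confidence. Read as at least one event, 1 − 0.85^10 = 0.803, which agrees. The present point does not depend on it.

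**Can the case arise under the text?** Take a weekly patient dosed on Day 1, whose Day 8 and Day 15 infusions are held for toxicity below DLT level, and who is next dosed on Cycle 2 Day 1 (Day 22).
- Delay of the Day 8 dose: 22 − 8 = 14 days. Delay of the Day 15 dose: 22 − 15 = 7 days. Both are within the 21 days of Section 5.4.
- Interval from the Day 1 dose: 22 − 1 = 21 days, which does not exceed the limit in Section 4.2.1.
- The patient has not discontinued, so 4.2.3 does not replace them and 7.4 does not exclude them. Section 3.2 counts them as treated.
- Drug received in Cycle 1: one third of plan. In the protocol's own example (50 µg/kg weekly against 150 µg/kg every three weeks), 50/150.

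This assumes that held infusions are skipped. Section 5.4 does not say so. If they shift, the patient may still receive all three, but then the end of Cycle 1, and with it the DLT window, is undefined.

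**How much easier is the level to clear?** Assumptions, none of them from the documents: full-exposure Cycle 1 DLT risk p between 0.20 and 0.50; equal, independent risk per infusion; any second cohort fully exposed.
- Risk after one of three infusions: q = 1 − (1 − p)^(1/3).
- Chance of clearing: P(0 of first 3) + P(1 of first 3) × P(0 of next 3).

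At p = 0.30:
- All fully exposed: 0.7^3 = 0.343; 3 × 0.3 × 0.7^2 = 0.441; 0.343 + 0.441 × 0.343 = 0.494.
- One patient with one infusion: q = 1 − 0.7^(1/3) = 0.112. P(0) = 0.888 × 0.49 = 0.435. P(1) = 0.112 × 0.49 + 0.888 × 0.42 = 0.428. Clearing: 0.435 + 0.428 × 0.343 = 0.582.

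Chance of clearing, by number of one-infusion patients in the first three:

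| p | q | none | one | two | three |
|---|---|---|---|---|---|
| 0.20 | 0.072 | 70.9% | 77.0% | 83.2% | 89.5% |
| 0.30 | 0.112 | 49.4% | 58.2% | 68.1% | 79.1% |
| 0.40 | 0.157 | 30.9% | 40.3% | 52.3% | 67.2% |
| 0.50 | 0.206 | 17.2% | 25.4% | 37.5% | 54.9% |

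One such patient adds about 6 to 9 points. The equal-risk assumption drives the size. For one such patient at p = 0.40, the result runs from 30.9% (no change) if all risk follows the first infusion to 46.4% if that patient carries no DLT risk. The column headed none is also the result if one-infusion patients are replaced by fully exposed ones.

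**Does the SAP expose the shortfall?** Only indirectly. Relative dose intensity covers the whole treatment period. One infusion in Cycle 1 followed by two full cycles gives 7 doses over (57 + 6)/7 = 9 weeks, or 7/9 = 78%, although Cycle 1 itself was at 33%. The dose-deviation examples in SAP 4.2 name doses more than 15% too high, not missed infusions.

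**The case against.** Several objections carry weight.

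- **The DLT-evaluable set does not drive escalation.** A reader of 7.4 might infer that this definition clears doses. It does not: 3.2 counts treated patients and never cites the set. Rewording 7.4 alone would change nothing in escalation. This stands, and it is why the gap has to be closed in three sections.
- **No planned estimate is biased.** A reader might infer a downward-biased DLT rate. The SAP plans no DLT rate or DLT table, so what is affected is escalation decisions and the reading of a listing.
- **Delayed is not the same as missed.** This also stands. The result holds only if delayed infusions are skipped.
- **The route is narrow.** Section 5.4 gives the first two cycles regardless of blood count recovery, and under 6.3.1 most non-hematologic events of Grade 3 or higher are DLTs anyway. What remains is mainly lower-grade non-hematologic toxicity. Escalation is also permissive, and the DESC decides on overall safety findings (6.3.2), so it could discount such a patient. No written rule requires it to.
- **The data are already listed.** SAP 4.7.1 would let a careful reader trace each patient's infusions. Only the link to DLT status is missing.

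Two further inferences fail. One is that the definition was written for three-weekly dosing and left unchanged when weekly dosing was added: the protocol gives amendment dates but no earlier text of 7.4. The other is that the chance of clearing rises from 34% to 70% at p = 0.30. Those are chances of zero DLTs in three (0.7^3 = 0.343, and 0.70 if all three patients had one infusion). They omit clearance by one in three followed by none in three, and the upper figure needs an unlikely cohort.

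**Conclusion.** The gap is real but limited. For weekly dosing, no rule on evaluability, replacement, escalation or MTD requires any share of the planned Cycle 1 drug, and the delay provisions do not rule out a patient who receives one of three infusions and still counts as DLT-free. The direction is toward easier clearance.

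The existence of the gap rests on the text, but the one-infusion case depends on delayed infusions being skipped. Its size rests on assumed risks: about 6 to 9 points for one such patient under equal risk per infusion, and nothing if all risk follows the first infusion.

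The documents do not show that any weekly patient missed an infusion, or that any level was cleared wrongly. With the trial stopped during Part 1, the remaining consequence is how DLT-free weekly patients are read in the report.

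**What to change.** **Now, in SAP 4.8.1.** Beside each patient's DLT status, list the Cycle 1 infusions given and the Cycle 1 dose received against plan. Flag DLT-free patients who were under-exposed, so that they are not read as full DLT-free observations. The data are already collected for SAP 4.7.1. Cost: one more listing column.

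**For any further weekly escalation, in Protocol 3.2, 4.2.3 and 7.4 together.**
- Define a DLT-evaluable patient as one who had a DLT, or who completed the observation period and received at least a pre-stated share of planned Cycle 1 drug. The share is for the Sponsor and DESC to set; none is proposed here.
- Replace patients who are not evaluable, and make the escalation and MTD rule count evaluable patients.
- State whether a delayed weekly infusion is skipped or shifts the cycle, so that the length of the DLT window is defined.

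Cost: wording in three sections and possibly a few replacement patients in weekly cohorts.

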4.1.8 End of Treatment Visit

The following procedures will be performed within 30 days (+ 7 days) after study treatment discontinuation:

- Serum or urine pregnancy test.
- Physical examination including whole body skin assessment.
- Weight and vital signs.
- ECOG performance status.
- Hematology, coagulation panel, and biochemistry parameters.
- Urinalysis and sample collection for assessment of additional renal function studies.
- 12-lead ECG.
- Sample collection for central laboratory assessment of PK and ADA.
- Whole blood sample collection for central laboratory analysis of peripheral WBC populations and evaluation of CD19 and other CD markers (e.g., CD20, CD21, CD22).
- MNC) samples:
 - Whole blood (WB) sample collection with subsequent MNC isolation for retrospective central laboratory evaluation of CD19 and other CD markers (e.g., CD20, CD21, CD22).

ADCT-402-102 Protocol Amendment 3

- Collection of AE information.
- Collection of concomitant medication information.
- Bone marrow sample for disease assessment (see Section 4.1.2.1).

4.1.9 12-week Follow-up Visit

Each patient will have a sample taken for assessment of PK and ADA at 12 (± 1) weeks after their last dose of ADCT-402.

Blood Sample Collection and Adverse Event Monitoring During Long-Term Follow-up

For all patients, a PK and ADA blood sample collection will be performed 12 weeks (± 1 week) following the last dose of ADCT-402.

For all patients, collection of AEs and SAEs will continue for up to 84 days (12 weeks) after the last dose of study drug or initiation of new anti-cancer treatment (see Section 6.3.3.2).

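### DLT evaluability in Protocol 7.4 depends on stopping drug in Cycle 1, not on dose received and days observed, so a fully dosed, fully followed DLT-free Q3W patient is excluded while the same patient with a DLT is kept

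*Protocol*

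**What the plan says.** Protocol Section 7.4 limits the DLT-evaluable set to Part 1 patients who receive study drug and "excludes patients who discontinue from the study drug during Cycle 1 without experiencing a DLT". It makes no exception for a patient who had the full Cycle 1 dose or was observed for the full window.

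Section 4.2.3 sets the replacement rule: "Any patient in Part 1 who discontinues before completion of the first treatment cycle, for any reason other than a DLT, is to be replaced". It does not say whether discontinuing refers to the drug or to the study.

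Section 3.2 gives the schedules. For Q3W: "Patients will be given ADCT-402 on Day 1 of each 3-week treatment cycle". For QW: "Patients will be given ADCT-402 QW on Days 1, 8 and 15 of each 3-week (21-day) treatment cycle". The DLT "observation period for dose-escalation is 1 cycle", that is, 21 days.

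Section 4.1.9 continues safety collection after drug is stopped: "For all patients, collection of AEs and SAEs will continue for up to 84 days (12 weeks) after the last dose of study drug". The sentence goes on to name the start of new anti-cancer treatment as another end point.

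Section 3.2 states the 3+3 and MTD rules in terms of the first 3 or first 6 *treated* patients. For the first QW dose it looks instead to Q3W patients who *completed* DLT observation.

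**The concern.** Evaluability for DLT should rest on two facts: whether the patient received the exposure under test, and whether the window was observed. Section 7.4 uses a third, whether drug was stopped during Cycle 1. For a QW patient who stops before Day 15, that is a fair proxy for incomplete exposure. For a Q3W patient it is not. Stopping drug between, say, Day 8 and Day 21 takes nothing away from Cycle 1 exposure and means only that Cycle 2 will not be given. If the same decision is dated Day 22, the patient stays in the set.

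The exclusion also depends on the outcome. Among fully observed patients who stop drug, those with a DLT stay in and those without one go out. If the Dose-Escalation Steering Committee (DESC) counts on this set, a dose level can look more toxic than it is. If Section 4.2.3 is read as stopping drug, a Part 1 place also goes to replacing someone whose 21-day DLT status was observed. Part 1 has about 40 places for up to 15 Q3W and 12 QW planned levels.

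**Working it through.** **The plan's own figure.** The only probability in the sample-size section (Protocol 7.3) is 80% for seeing an AE among 10 patients at a true rate of 15%. Read as at least one AE, it reproduces: 1 − 0.85^10 = 0.803. It concerns Part 2 cohorts and does not bear on this point. The documents give no DLT rate, evaluable fraction or replacement rate.

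**Can the patient exist under the text?** Take a Q3W patient dosed on Day 1 only. AE collection may run to Day 1 + 84 = Day 85 unless new anti-cancer treatment starts, so the 21-day window can be covered after drug is stopped. Under Section 3.2 this patient is treated and can have completed DLT observation. Under Section 7.4 the patient is not evaluable.

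**Bias for fully observed patients.** Let p be the true DLT rate, and d the share of DLT-free patients who stop drug in Cycle 1 but are observed through Day 21 without new therapy. Both are assumptions.

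- Evaluable-set rate: r = p / [p + (1 − p)(1 − d)]
- Chance a level clears 3+3 (0/3, or 1/3 then 0/3): (1 − r)^3 + 3r(1 − r)^5
- Patients treated per 3 evaluable, if all those dropped are replaced: 3 / [1 − d(1 − p)]

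Example at p = 0.20, d = 0.20: r = 0.20 / (0.20 + 0.80 × 0.80) = 0.20 / 0.84 = 0.238; clearance 0.626; treated per 3 evaluable = 3 / 0.84 = 3.57.

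| p | d | r | Clearance | Treated per 3 evaluable |
|---|---|---|---|---|
| 0.20 | 0 | 0.200 | 0.709 | 3.00 |
| 0.20 | 0.05 | 0.208 | 0.691 | 3.12 |
| 0.20 | 0.10 | 0.217 | 0.671 | 3.26 |
| 0.20 | 0.20 | 0.238 | 0.626 | 3.57 |
| 0.20 | 0.30 | 0.263 | 0.572 | 3.95 |
| 0.30 | 0 | 0.300 | 0.494 | 3.00 |
| 0.30 | 0.05 | 0.311 | 0.472 | 3.11 |
| 0.30 | 0.10 | 0.323 | 0.449 | 3.23 |
| 0.30 | 0.20 | 0.349 | 0.399 | 3.49 |
| 0.30 | 0.30 | 0.380 | 0.343 | 3.80 |

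The clearance column assumes that cohorts are filled with evaluable patients.

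**When observation ends at stopping.** Suppose stopping is independent of DLT risk, with λ = −ln(1 − p), μ = −ln(1 − d), where d is now the chance of stopping within the window. The chance of an observed DLT is a = λ/(λ + μ) × [1 − e^−(λ+μ)]. Excluding DLT-free stoppers gives a / [a + e^−(λ+μ)]; counting them as DLT-free gives a. At p = 0.20 and d = 0.10 to 0.30, exclusion gives 0.209 to 0.232 and counting them as DLT-free gives 0.190 to 0.169. Neither recovers 0.20.

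**When stopping is informative.** If 20% stop with their DLT status unseen, with a would-be DLT risk of 0.50 in them and 0.20 in the rest, the true rate is 0.20 × 0.50 + 0.80 × 0.20 = 0.26, while the evaluable set shows 0.20. The sign reverses.

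**The case against.** A reader might infer that the DLT rate in this trial is overstated and the MTD biased downward. The documents do not support that, for these reasons.

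- **Link to escalation.** No section says that escalation uses the Section 7.4 set. The 3+3 and MTD rules count treated patients, under DESC oversight. If applied literally they count the dropped patient and this bias does not arise; only the replacement rule suggests otherwise. This stands, and it makes the mismatch between sections part of the point.
- **Replacement.** Section 4.2.3 sits under withdrawal from the study. If it means leaving the study, a patient off drug but still followed is not replaced, and the last column of the table falls away.
- **Follow-up.** AE collection can end at new anti-cancer treatment. After drug is stopped, the visit called for is End of Treatment, within 30 (+7) days and whenever possible. No text requires the Day 8 or Day 15 assessments after stopping, and there is no Day 21 visit. Full observation therefore has to be documented, not presumed.
- **Frequency.** Early progression is a weak example: Section 6.1 defines PD only after a response, and the first on-treatment marrow is before Cycle 3. Section 4.2.1 allows other reasons for stopping, but no frequency is given. Values of d from 10% up have no support in the documents, so 5% is shown too.
- **Hematologic DLTs.** Section 6.3.1 requires 6 or 8 weeks of cytopenia, so 21 days of follow-up does not settle these. Only status over the 21-day window is known.
- **Net direction.** The set also keeps QW patients who miss doses without discontinuing, which pushes the other way.
- **Reporting.** The SAP, written after early termination in Part 1, defines only the Safety set (4.1.1) and lists DLTs (4.8.1).

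None of this supplies the missing exception in Section 7.4 for a fully dosed, fully observed Q3W patient.

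**Conclusion.** The concern holds in a limited form. On its literal wording, Section 7.4 makes inclusion of a fully dosed, fully followed Q3W patient who stops drug in Cycle 1 depend on whether a DLT occurred, and for those patients the DLT fraction is biased upward. Sections 3.2, 4.2.3 and 7.4 also use different bases for who counts.

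The size is unknown. At an assumed true rate of 20%, the range runs from nearly nothing (20.8%, clearance 69%, if 5% of DLT-free patients are affected) to material (26.3%, clearance 57%, at 30%). This rests on observation through Day 21, no new therapy, and a DESC that counts evaluable patients. Needless replacement follows only if Section 4.2.3 means stopping drug. For patients who leave observation early or stop for emerging toxicity, the direction is not established, and excluding unobserved or under-dosed DLT-free patients is defensible. Any effect would have been on Part 1 counting and enrolment; no DLT rate planned in the SAP is altered.

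**What to change.** In Section 7.4, define the DLT-evaluable set as Part 1 patients who either had a DLT within the observation period, or received all planned Cycle 1 study drug and had safety follow-up to the end of the 21-day window with no new anti-cancer therapy, whether or not later cycles were given. Reconcile Section 3.2 (treated, or completed observation) and Section 4.2.3 (drug or study discontinuation) with that definition. Because the trial has ended, the report could state, beside the DLT listing, the Cycle 1 dose received and days observed for each patient treated as non-evaluable or replaced.

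The cost is wording, plus a DESC check of follow-up and new-therapy dates. The downside is that a patient off drug without documented follow-up through Day 21 remains non-evaluable, as does a QW patient who did not receive all planned Cycle 1 infusions and had no DLT.
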